5.2.2 KNOWN POTENTIAL BENEFITS

The subject may benefit from treatment in the GSM brace in terms of curve correction, curve stabilization and increased comfort (relative to their standard of care TLSO) while wearing the GSM brace, although the potential for longer-term benefit is unknown.

5.2.3 ASSESSMENT OF POTENTIAL RISKS AND BENEFITS

This study presents minimal risk with the potential for benefit.

5.3 MEASURES TO MINIMIZE BIAS: RANDOMIZATION AND BLINDING

It will not be possible to blind the subject or the assessors to the study condition (type of brace) due to their unique characteristics (which is also visible in the radiographs). All radiographic measurements will be made by the site PI's or their delegates and verified by the medical advisor ([name]).

5.4 COMPLIANCE WITH STUDY INTERVENTION

The use of the device will be primarily monitored via the temperature monitor data. A secondary aim involves using the temperature monitor data to validate inferences about compliance using data from the force and accelerometer sensors built into the GSM brace.

5.5 CONCOMITANT THERAPY

Subjects will be encouraged to continue with any concomitant therapy and activities during the study (e.g. physical therapy, chiropractic, massage, yoga, school, sports).

5.6 COMPENSATION TO SUBJECTS

Subjects will be compensated \$25 after visits 1 and 2, \$25 for Visit 3 and then \$10 for each additional week during the 3 month period (10 weeks), for a possible total compensation of \$175. Payment will be issued within 1 month after Visit 2, and within 1 month after the subject exits the study. Payments will be pro-rated according to the number and type of visits completed.

6 STUDY INTERVENTION DISCONTINUATION AND PARTICIPANT DISCONTINUATION/WITHDRAWAL

6.1 DISCONTINUATION OF STUDY INTERVENTION

The intervention will be halted by the investigators if:

1. Equivalent or improved in-brace correction is not obtained at the Week 1 visit
2. If the subject is not able/willing to wear the GSM brace for approximately the same number of hours as the TLSO
3. Safety concerns are noted by the PI, study staff and/or the medical monitor
4. Radiographic evaluation at Visit 3 suggests that the curve is not stable (has progressed more than 10 degrees)
5. If the parent/subject, investigator or medical monitor feel that continuation of treatment in the GSM brace is not in the best interests of the subject. Ongoing care will be individually determined based on standard of care considerations.

Once the GSM brace is discontinued, continued follow-up for safety and efficacy are not required.

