2 OBJECTIVES AND ENDPOINTS

Primary

1. Safety of the GSM brace: To identify unanticipated adverse events associated with the GSM brace and patient characteristics likely to raise safety issues
2. Performance of the GSM brace:
 - a. To assess immediate radiographic outcomes (in-brace Cobb angle) relative to those in the TLSO
 - b. To assess short-term radiographic outcome (out of brace Cobb angle) after 3 months
 - c. To assess adherence to the bracing prescription (hours of wear per day)
 - d. To assess patient-reported outcomes including health-related quality of life and measures of acceptability of the GSM brace (e.g. comfort, stress, interference with activities) relative to experiences in the patient's previous TLSO

Secondary

1. To assess spinal range of motion in the GSM brace relative to the subject's TLSO
2. To assess lung vital capacity in the GSM brace relative to the subject's TLSO
3. To validate accelerometer data (obtained from an embedded sensor in the GSM brace) as an estimate of the average hours of wear per day.

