Ongoing Evaluations after Visit 3 (following the standard-of-care until GSM brace is discontinued)

For subjects continuing to use the GSM brace after Visit 3: Subject clinical care and evaluations (x-rays, clinical exams) after Visit 3 will be limited to that typically performed as the standard of care (SOC). The exception to the SOC will be the administration of the BrQ and ISYQOL at the end of treatment, ongoing monitoring and recording of AE's discovered during routine clinic visits or other communications, and temperature monitoring (at sites where this is not typically SOC). Clinical and radiographic data from these visits will be collected for study purposes (height, weight, onset of menses, Cobb angle(s), kyphosis, lordosis, coronal and sagittal balance, apical vertebral rotation, in-brace Cobb angle(s), and skeletal maturity indicators) as available.

GSM brace treatment will be discontinued using individualized SOC parameters such as Cobb angle and skeletal maturity indicators, at which time the subject will exit the study.

Exit From Study

Subjects will exit the study upon occurrence of the following events

1. Visit 2. GSM in-brace Cobb is $>10^\circ$ more than the TSO in-brace Cobb
2. Subject not wearing or tolerating GSM brace (per temperature monitor reading 2 weeks after baseline, or at any time during study period)
3. Visit 3. GSM out-of-brace Cobb indicates curve progression
4. GSM brace is discontinued using standard of care criteria

Additional Information on Assessments

Radiographs and Assessments: When available, radiographs will be obtained using the EOS® Imaging system Micro Dose protocol. The EOS® system provides low dose, full body, stereoradiographic images of patients in a functional position. It is a bi-planar device using two perpendicular fan beams of X-rays and proprietary detectors that travel vertically while scanning the patient. In a few seconds, the EOS® exam produces two simultaneous frontal and lateral, low dose images of the whole body or an anatomical segment. The Micro Dose option for pediatric follow up exams further reduces the radiation exposure. <http://www.eos-imaging.com/us/professionals/eos/eos>.

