7.3 CLASSIFICATION OF AN ADVERSE EVENT

7.3.1 SEVERITY OF EVENT

Mild = not requiring treatment

Moderate = resolved with treatment

Severe = unable to carry on normal activities and required professional medical attention

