7.3.4 TIME PERIOD AND FREQUENCY FOR EVENT ASSESSMENT AND FOLLOW-UP

AE's will be solicited at each study visit, during the scheduled phone contacts and as often as daily via subject report on the questionnaires

Unsolicited AE's may be identified via observations and general discussions with the subject and/or parent at the study visits

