8.4 STATISTICAL ANALYSES

This is a pilot study and no formal hypothesis testing will be done.

Descriptive statistics of selected variables will be calculated.

Primary Aims

1. Safety of the GSM brace: Summary of all adverse events; number and nature of adjustments made to the GSM brace
2. Performance of the GSM brace:
 - a. Difference between in-brace Cobb angle measurements obtained in each brace
 - b. Difference in out of brace Cobb angles (pre- and 3 months post-GSM brace)
 - c. Average hours of wear per day relative to the prescription and to historical wear data (from chart and temperature monitor)
 - d. Change in BrQ and ISYQOL scores baseline to 3-month visit; summary of GSM acceptability during various activities and qualitative analysis of free text entries recorded in GSM Brace Diary

Secondary Aims

1. Difference in range-of-motion testing between TLSO and GSM brace
2. Difference in vital capacity testing between TLSO and GSM brace

3. Correlation of accelerometer data and temperature monitor data; development and testing of an algorithm to convert accelerometer data to an estimate of the average hours of wear per day.

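### No section requires follow-up of adverse events still open when the GSM brace is discontinued, although safety is the first primary aim

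*Combined protocol and SAP*

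**What the plan says.** Section 2 lists safety as primary objective 1: "Safety of the GSM brace: To identify unanticipated adverse events associated with the GSM brace and patient characteristics likely to raise safety issues". The matching analysis in Section 8.4 is "Summary of all adverse events; number and nature of adjustments made to the GSM brace".

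Section 6.1 lists the reasons for halting the brace. Item 3 is "Safety concerns are noted by the PI, study staff and/or the medical monitor". After the list comes the sentence at issue: "Once the GSM brace is discontinued, continued follow-up for safety and efficacy are not required".

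Section 5.1.2 (Exit From Study) makes failure to wear or tolerate the brace an exit event at any time. For subjects who continue after Visit 3 and later stop under standard-of-care criteria, brace discontinuation is the point "at which time the subject will exit the study".

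On collection, Section 7.3.4 says "AE's will be solicited at each study visit, during the scheduled phone contacts", and as often as daily through questionnaires. Section 7.3.1 grades severity, with "Moderate = resolved with treatment". Section 7.3.7 requires related or possibly related events graded moderate or severe to be reported by phone to subjects then wearing the GSM brace.

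**The concern.** In a small, uncontrolled first field test, the events that make someone stop the device carry much of the safety information. Section 1.1 (Study Rationale) says the brace had until then been tested only in the lab on healthy volunteers, and the subjects are aged 10 to 15. Under Section 6.1, the decision that takes a subject off the brace for a safety reason also ends any requirement to observe what happens next.

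Three things are at stake: the completeness of the adverse event summary for subjects who stop, the severity grade of events still open at that point, and the notice to other wearers that depends on the grade. Early exits are also replaced (Section 8.1). The 10 to 30 completers are therefore in part selected for tolerating the brace, while those who stopped may have the least complete safety record.

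**Working it through.** No arithmetic applies. The plan gives no adverse event rate, no exit rate and no sample size calculation, so there is no figure to reproduce. The check is whether any other section restores what Section 6.1 waives, and which of the plan's own rules depend on it.

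**Step 1: does another section require follow-up of open events?**

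- *5.1.2, phone visits (weeks 2, 4, 6, 8 and 10) and Visit 3.* Each has a Safety Check, but the calls concern how the subject is adapting to the GSM brace. No contact is set for someone who has stopped.
- *5.1.2, after Visit 3.* Adverse event monitoring is described only for subjects still using the brace.
- *6.2.* A subject who wants to stop tells staff so that the TLSO can be resumed. No safety contact follows.
- *6.3.* Calls at 2 weeks and at least monthly serve retention and event queries. No call after discontinuation is named, and 6.1 waives it.
- *7.3.4.* The heading includes follow-up, but the text covers only how events are solicited or noticed. It has no post-exit window and no rule for open events.
- *7.3.5 and 7.3.6.* Recording and reporting run from identification. Neither section asks for a later outcome.

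None of these restores the duty.

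**Step 2: which rules depend on an event's later course?**

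Take a pressure sore, which Section 7.2.1 lists as anticipated, still open when the brace stops.

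- *Untreated so far.* It fits Mild. If it is treated later and resolves, the definition makes it Moderate, but nothing requires anyone to find that out.
- *Under treatment, unresolved and not disabling.* It fits no grade. Mild excludes treatment, Moderate needs resolution, and Severe needs loss of normal activity together with professional medical care.
- *Disabling and under medical care.* It can be graded Severe at exit, so nothing is lost on grade.

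In the first two cases the Section 7.3.7 notice turns on information the site need not obtain. The 48-hour clock in Section 7.3.6 for unanticipated serious events likewise starts at identification, and after exit no scheduled contact exists at which identification would occur.

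**Step 3: how many events?**

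The relevant count is subjects who stop the brace with an event open, plus those in whom an event from GSM wear first appears afterwards. The documents give nothing from which to estimate either.

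**The case against.** Much of the opposing case stands.

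- *Not required is not forbidden.* A reader might infer that events causing an exit have no recorded outcome, or that the site never learns whether they healed. The documents do not support that. Subjects are existing patients of the study centers (4.3) and go back to a TLSO, and ongoing care is decided individually (6.1, item 5). The site may well see the outcome. The gap is that nothing obliges it to enter what it sees as study data, so completeness may differ between sites.
- *The events themselves are not lost.* Section 7.3.5 puts them on the case report form, sends them to the sponsor on identification and to the medical monitor every 2 weeks. The form is not in the documents, so it may already hold an outcome field.
- *Exit need not be immediate.* For wear-time problems the investigator first considers adjustment (5.1.2), and staff try modifications (6.2). Some events will be assessed, or settled, before exit.
- *Only Moderate depends on resolution.* That definition is loose for on-study events too, and is partly a separate drafting matter.
- *The aim speaks of identifying unanticipated events.* Identification does not always need an outcome. But the analysis is a summary of all events, and finding patient characteristics that raise safety issues is easier when it is known how events turned out.
- *Return to a TLSO blurs attribution.* Section 5.2.1 says TLSOs themselves cause skin events. Resolution or persistence after exit is therefore weak evidence on relatedness, and a later call will pick up some TLSO events. The fix has to allow for this.
- *Size.* It is tempting to assume an exit rate. With 20% to 30%, exits would run from 10 × 0.2/0.8 = 2.5 to 30 × 0.3/0.7 = 12.9. That rate is not in the documents, and the count includes exits for poor in-brace correction or low wear time, which need involve no adverse event. It does not measure this problem.

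Finally, the plan classes the device as external and non-significant risk, in a descriptive pilot. That argues for light follow-up, not for none.

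**Conclusion.** The point holds in limited form. Section 6.1 expressly waives safety follow-up once the GSM brace stops, and no other section requires open events to be followed. Events leading to discontinuation are recorded and reported when identified. Their later resolution, treatment or progression to a serious event need not be captured, although the first primary aim, the Moderate grade and the Section 7.3.7 notice all bear on it.

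The number of events affected is unknown and may be zero, and the documents do not show that the safety summary will be biased by any stated amount. The conclusion rests on the text alone, read with sites doing what is required and no more. The change should be made because it is cheap and serves the trial's first aim. It does not call the design into question.

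**What to change.** Keep efficacy follow-up after discontinuation optional. For safety, replace the Section 6.1 sentence and add matching text to Section 7.3.4:

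1. Any adverse event open when GSM is discontinued is followed, by phone or from routine clinic records, until resolved or stable.
2. Every subject who stops GSM gets one closing call using the existing Safety Check query, at an interval fixed in advance by the sponsor.
3. The adverse event form records outcome, its date, and the brace in use (GSM or TLSO) at onset and at resolution, so that events arising after return to the TLSO are not attributed to GSM.
4. The Section 8.4 summary shows outcome and covers all subjects fitted with the GSM brace, including those replaced under Section 8.1.

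This adds no visit or radiograph and changes no treatment or stopping rule. The cost is one call per subject who stops, further contact only for open events, and a few lines of text and form fields. Some families will not be reached, and some events collected after exit will reflect the TLSO. Item 3 lets the summary separate those.

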6.2 PARTICIPANT DISCONTINUATION/WITHDRAWAL FROM THE STUDY

1. Participants will be withdrawn from the study in the event of a positive pregnancy test or reports of a suspected pregnancy.
2. Participants may withdraw voluntarily from the study or discontinue use of the GSM brace at any time. Participants who wish to stop wearing the GSM brace will be instructed to notify study staff so that treatment can be resumed using the TLSO brace.

Participants will be instructed to contact the study staff (PI, orthotist or coordinator) at any time to discuss issues they may be having with the GSM brace or with any other aspect of the protocol. Study staff will attempt to make any modifications to the brace or other aspects of the protocol necessary to mitigate these issues and maintain the participant on protocol.

6.3 LOST TO FOLLOW-UP

Participants will be considered lost to follow-up if they cease to report for study visits and do not respond to our attempted contacts. Staff will contact participants by phone at 2 weeks after GSM brace initiation and at least monthly to address questions and issues. Subjects will be queried for any questions or concerns, and for the occurrence of anticipated and unanticipated adverse events.

Study staff will accommodate the participants' schedule in order to minimize missed study visits. In the case of a missed visit, staff will attempt contact via three phone calls and/or emails each 1 week apart.

Completion of the questionnaires and diaries will be encouraged but not required.

7 STUDY ASSESSMENTS AND PROCEDURES

7.1 PERFORMANCE ASSESSMENTS

1. Primary performance measures
 1. Visit 2 GSM in-brace Cobb angle compared to that in the TLSO at baseline
 2. Visit 3 out of brace Cobb angle compared to measurements from the most recent out of brace radiograph
 3. Average hours of GSM brace wear per day over the 3-month trial period (temperature monitor data)
 4. Change in scores on the Brace Questionnaire and the ISYQOL
2. Secondary measures
 1. Vital capacity and range-of-motion relative to that obtained in the TLSO at Visit 1
 2. Accelerometer data (obtained from an embedded sensor in the GSM brace) as an estimate of the average hours of wear per day (to be validated by comparison with temperature monitor data)

7.2 SAFETY ASSESSMENTS: ADVERSE EVENTS AND SERIOUS ADVERSE EVENTS

Safety will be monitored continuously during the trial

7.2.1 DEFINITION OF ADVERSE EVENTS (AE)

The following AE's are anticipated and related or possibly related to brace wear or to the diagnosis of AIS:

- Skin Issues (on the trunk, shoulders or any other area in contact with the brace): bruising, lacerations, ulcers, pressure sores, rash. Most skin issues are classified as mild and can be alleviated by minor adjustments to the brace.
- Back pain
- Anxiety
- Problems sleeping
- Shortness of breath
- Altered body image or self-esteem

7.2.2 DEFINITION OF SERIOUS ADVERSE EVENTS (SAE)

Death

Life-threatening conditions

Hospitalization

Disability

A condition requiring intervention to prevent permanent impairment/damage

7.3 CLASSIFICATION OF AN ADVERSE EVENT

7.3.1 SEVERITY OF EVENT

Mild = not requiring treatment

Moderate = resolved with treatment

Severe = unable to carry on normal activities and required professional medical attention

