7.3.5 ADVERSE EVENT REPORTING

Events will be recorded on the Adverse Event case report form as they are identified

All events will be reported to the sponsor upon identification

All unanticipated events will be reported to the IRB on continuing review applications or close of study (or according to local IRB policy).

Adverse event forms will be sent to the medical monitor every 2 weeks during the study, who will then summarize the AE's in a report to the sponsor and IRB.

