7.3.6 SERIOUS ADVERSE EVENT REPORTING

All unanticipated serious adverse events will be reported within 48 hours of identification to the sponsor, medical monitor and the IRB (or as required using local standards)

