7.3.7 REPORTING EVENTS TO PARTICIPANTS

All moderate or severe, possibly related or related events will be reported to subjects who are currently wearing the GSM brace via a phone call from the PI within 48 hours of identification

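### The severity grades leave some events that require treatment ungraded and call some incapacitating events mild, so the 48-hour call to brace wearers can be missed

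*Combined protocol and SAP*

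**What the plan says.** Section 7.3.1 (Severity of Event) defines three grades and nothing else:

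- "Mild = not requiring treatment"
- "Moderate = resolved with treatment"
- "Severe = unable to carry on normal activities and required professional medical attention"

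It gives no default grade and no rule for an event that is still open.

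Section 7.3.7 (Reporting Events to Participants) uses the grade as a trigger: "All moderate or severe, possibly related or related events will be reported to subjects who are currently wearing the GSM brace", and this is to happen "via a phone call from the PI within 48 hours of identification".

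The other reporting routes do not use the grade. Section 7.3.5 states "All events will be reported to the sponsor upon identification", and sends adverse event forms to the medical monitor every 2 weeks. Section 7.3.6 states "All unanticipated serious adverse events will be reported within 48 hours of identification to the sponsor, medical monitor and the IRB", subject to local standards.

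**The concern.** Each grade is built on a different attribute. Mild depends on whether treatment is needed, moderate on how treatment turned out, and severe on function and professional attention together. Definitions built this way need not cover every event, and they need not be mutually exclusive.

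The timing adds to the problem. Moderate can be assigned only once an event has resolved, but the call to current wearers is due within 48 hours of the event being identified. A brace-related pressure sore that is under treatment, still open at 48 hours and not stopping normal activities has no qualifying grade when the call is due. If it heals later it becomes moderate, but by then the 48 hours have passed. If the subject leaves the brace with the sore unhealed, resolution may never be recorded, because section 6.1 does not require follow-up after discontinuation.

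What is at stake is a participant-protection step in a study of girls aged 10 to 15, and consistent grading across several sites. Section 7.2.1 lists ulcers, pressure sores, back pain, anxiety and sleep problems as anticipated, and any of these can persist under treatment.

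**Working it through.** The plan gives no figure for this point, and none of the usual sample size inputs applies (section 8.4: "This is a pilot study and no formal hypothesis testing will be done"). The check is a cross-classification of the definitions.

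**Inputs.** The three grades are from section 7.3.1 and the trigger from section 7.3.7. Every event is taken as possibly related or related, since unrelated events fall outside the call by design.

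**Combinations.** Treatment has four states: not required; required but not given; given by a non-professional; given by a professional. Crossing these with resolved (no/yes) and normal activities prevented (no/yes) gives 4 × 2 × 2 = 16. Professional medical attention is taken to mean professional treatment was given.

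| Treatment | Resolved | Activities maintained | Activities prevented |
|---|---|---|---|
| Not required | no or yes | mild, no call | mild, no call |
| Required, not given | no or yes | no grade, no call | no grade, no call |
| Non-professional | no | no grade, no call | no grade, no call |
| Non-professional | yes | moderate, call | moderate, call |
| Professional | no | no grade, no call | severe, call |
| Professional | yes | moderate, call | moderate and severe, call |

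Each cell in the first two rows stands for two combinations.

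**Counts.**
- No grade: 4 (required, not given) + 2 (non-professional, unresolved) + 1 (professional, unresolved, activities maintained) = 7.
- Two grades: 1.
- No call: 4 mild + 7 ungraded = 11. Two of the 11 are plainly mild (no treatment required, activities maintained), which leaves 9 where the missing call is questionable.
- Treated and unresolved: 3 of 4 have no grade. The fourth meets both severe conditions and triggers the call.
- Activities prevented and no treatment given: 4 combinations. The 2 where treatment was not required are mild; the 2 where it was required have no grade. None triggers the call.

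**Sensitivity to the reading of the severe grade.** Professional attention could instead be read as needed, whether or not received. If every event that prevents activities and requires treatment is taken to need it, 3 ungraded combinations become severe. That leaves 7 − 3 = 4 without a grade and 11 − 3 = 8 without a call. All 4 are events requiring treatment with activities maintained, and 3 of those 4 are unresolved. Conversely, an event that prevents activities and is assessed professionally but needs no treatment would meet both the mild and the severe definitions. The gap narrows or shifts with the reading but does not close.

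**Other routes.** Section 7.2.2 lists disability as a serious adverse event, but section 7.3.6 covers only unanticipated serious events and is addressed to the sponsor, medical monitor and IRB. Section 7.3.5 is also addressed to oversight bodies. Neither reaches participants, so section 7.3.7 is the only route affected and nothing stands in for it.

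**The case against.** The strongest reply is that a sensible investigator would read the three lines as a ladder: no treatment, treatment, then incapacity with medical care. On that reading a treated, open event would be called moderate. This is plausible, but the text does not say it, and different sites may apply it differently.

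Safety oversight also does not hang on the grade. Every event goes to the sponsor, the medical monitor sees the forms every 2 weeks, and section 6.1 lets the investigator, staff or monitor halt treatment over a safety concern. That stands, and it confines the point to grading and the participant call.

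A reader might infer more than the documents support, in four ways:

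- That every treated, unresolved event is ungraded. An event meeting both severe conditions is severe and triggers the call.
- That any incapacitating event left untreated is mild. The criterion is that treatment was not required; one that needed treatment but received none has no grade.
- That any skin event taking longer than 48 hours to heal is ungraded. One that needs no treatment is mild however long it lasts, and section 7.2.1 expects most skin problems to be mild.
- That the primary safety analysis rests on these grades. Section 8.4 plans an overall adverse event summary and a record of brace adjustments, with no breakdown by severity. The safety objective in section 2 concerns unanticipated events and patient characteristics.

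**Conclusion.** The point holds in a limited form. As written, the grades are neither exhaustive nor mutually exclusive, and the definition of moderate cannot work with a clock that starts at identification. The consequence is that a related event that is still open and requires treatment, or that prevents normal activities without requiring treatment, can miss the call to current wearers.

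The size is 7 of 16 combinations ungraded and 11 of 16 without a call under the stated reading, or 4 and 8 under the more generous one. The documents give no event rates, so the number of subjects or calls affected in a study of 10 to 30 completers (section 8.1) cannot be estimated. The conclusion assumes that the definitions are applied literally. It does not imply that the sponsor, medical monitor or IRB would go uninformed, or that the planned safety summary is invalid.

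**What to change.** Take outcome out of section 7.3.1 and make the grades exhaustive and non-overlapping:

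- Mild: no treatment required and normal activities maintained.
- Moderate: treatment required, resolved or not, or normal activities prevented, but not meeting the severe definition.
- Severe: as now.

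Applied to the same 16 combinations, this gives 2 mild, 2 severe and 16 − 2 − 2 = 12 moderate. Each combination has exactly one grade, and 14 rather than 5 would trigger the call if related. Classing incapacitating events that need no treatment as moderate matters: barring them from mild without placing them elsewhere would only move them to no grade.

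In section 7.3.7, start the 48 hours when an event is first identified as moderate or severe, including when an event first graded mild worsens. Fixing the trigger to the grade at first identification would miss events that worsen. Record resolved or ongoing as a separate item if the adverse event form, which is not among the documents, does not already do so.

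The cost is a few lines of protocol, possibly one form field, and a few more calls to participants. No visit or assessment is added.
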